5.2.5.4 Other events to be reported

Changes in vital signs, physical examination, and laboratory test results

Changes in vital signs, physical examination and laboratory test results will be recorded as an AE or SAE in the (e)CRF , if they are judged clinically relevant by the investigator.

Worsening of the underlying disease or other pre-existing conditions

Worsening of the underlying disease or of other pre-existing conditions will be recorded as an AE or SAE in the (e)CRF through the Follow-Up period.

Overdose

Any overdose defined as any higher dose than prescribed for the individual patient must be reported on the adverse event form of the eCRF book. AEs originating in the overdose must be documented on a separate line.

Pregnancy

Pregnancy Test or Confirmation of Birth Control: Performed at indicated study visits ([Table 1](#)). Record of a pregnancy test or confirmation of birth control will be recorded as available at each study visit. This information will be kept in the source documents and not recorded in the eCRF.

Once a female patient has been enrolled into the clinical trial and has received study medication, the investigator must report immediately any drug exposure during pregnancy to the sponsor appointed CRO. Drug exposure during pregnancy has to be reported immediately (within 24 hours or next business day whichever is shorter) by the treating physician or designee to the sponsor appointed CRO when the treating physician or designee first becoming aware of the occurrence. The outcome of the pregnancy associated with the drug exposure during pregnancy must be followed up through to resolution. In the absence of an AE or SAE, only the Pregnancy Monitoring Form for Clinical Trials must be completed.

If an SAE occurs in conjunction with the pregnancy, then the reporting time frame for an SAE (within 24 hours or next business day whichever is shorter) must be met. The SAE form is to be completed. The sponsor or designee will provide instructions on how to collect pregnancy information. Follow-up, information on the outcome of the pregnancy is also required be forwarded to the sponsor's designee. The ISF will contain the Pregnancy Monitoring Form for Clinical Trials.

5.3 IMMUNOGENICITY (ANTI-DRUG ANTIBODY)

ADA samples will be collected at approximately 15 min. before Neihulizumab administration on Day 1, Day 29, Day 57 and also at EOT (Day 84), 28, 56 and 98 days after EOT (Days 112, 140 and 182) for each patient in a non-anticoagulant serum drawing tube to produce about 1.0 mL of serum. Instructions for handling and shipping specimens will be provided in detail in the Laboratory Manual.

5.4 PHARMACOKINETICS END POINTS

If feasible, the following PK parameters will be calculated:

Day 1, Day 50 and Day 78: C_{max} and associated parameters

For quantification of analyte plasma concentrations, PK blood samples will be taken from a forearm vein in an EDTA (ethylenediaminetetraacetic acid)-anticoagulant blood drawing tube at the time points specified in [Table 1](#).

Instructions for handling and shipping specimens will be provided in detail in the Laboratory Manual.

5.5 OTHER ASSESSMENT (S)

A medical examination will be carried out within 28 days before visit 2 (i.e., during the screening period before the infusion of Neihulizumab). Screening activities will include documentation of information provided to patients, informed consent, review of demographics including weight, relevant medical history, ulcerative colitis history, concomitant medication, inclusion/exclusion criteria, vital signs (BT, BP, PR, RR, and oxygen saturation), 12-lead ECG and laboratory (including safety, drug and viral screening, stool screening, QuantiFERON[®] test and pregnancy), physical examination, flexible sigmoidoscopy, complete Mayo Clinical Score, IBDQ, biomarkers (fecal calprotectin and CRP), and histopathological analysis. The weight will be reassessed before administration of Neihulizumab in order to confirm the dosage. The EOS examination will include physical examination, vital signs, flexible sigmoidoscopy, complete Mayo Clinic Score, IBDQ, biomarkers (fecal calprotectin and CRP), histopathological analysis, safety lab, ADA test and pregnancy.

5.6 APPROPRIATENESS OF ASSESSMENTS

All assessments performed during this trial are standard and will be performed in order to monitor efficacy and safety aspects relevant to Neihulizumab administration in an appropriate way. The scheduled assessments are appropriate to observe drug related changes over time. Therefore, all assessments taken in this trial are appropriate.

5.7 BIOMARKERS

Biomarker studies for faecal calprotectin and c-reactive protein (CRP) will be performed to monitor ulcerative colitis activities.

5.8 PHARMACODYNAMICS

5.8.1 Pharmacodynamic endpoints

None.

5.9 PHARMACOKINETIC - PHARMACODYNAMIC RELATIONSHIP

Not applicable.

6. INVESTIGATIONAL PLAN

All patients must provide written informed consent before any study-specific procedures or assessments are performed. Day 1 (Visit 2) will occur as soon as possible and within 28 days after the initial screening visit (Visit 1) has verified eligibility and documented informed consent.

6.1 VISIT SCHEDULE

6.1.1 Screening period

After the patients have been informed about the trial, all patients will have given their **written informed consent** in accordance with GCP and the local legislation prior to enrolment to the study. The following Screening laboratory tests/evaluations will be performed within 4 weeks (28 days) prior to the infusion of Neihulizumab (Week 0). A single retest for screening laboratory retest is allowed per investigator's discretion.

- Assignment of patients number
- Review of inclusion and exclusion criteria
- Demographic data (e.g., sex, age, race/ethnicity)
- Complete medical history
- Patient ulcerative colitis history
- Concomitant medications
- Complete physical examination-including weight and vital signs.
- 12-lead ECG
- Safety lab tests (Hematology and Chemistry)
- Urinalysis
- Drug and viral screening
- Serum pregnancy test, if applicable
- Provide and review the diary instruction and diary sheet to patients
- Flexible sigmoidoscopy
- Collect the filled diary card from patient
- Physician Global Assessment
- Complete Mayo Clinic Score assessment
- Histopathological analysis
- IBDQ assessment
- Stool screening
- Fecal calprotectin and CRP tests

- HbA1c test
- QuantiFERON[®] test for Tuberculosis

6.1.2 Study period

Patients who meet the inclusion/exclusion criteria will receive one dose of Neihulizumab intravenously starting from Day 1 (Week 0). It is preferred but not required that the drug administration should occur at the similar time of each visit day. See [Appendix 10.1](#) for the detailed procedures for preparing Neihulizumab for intravenously administration. Administration of the study drug will be repeated on Day 8 (Week 1), Day 15 (Week 2), Day 22 (Week 3), Day 29 (Week 4), Day 36 (Week 5), Day 43 (Week 6), Day 50 (Week 7), Day 64 (Week 9), and Day 78 (Week 11).

The measurements performed during the study period are specified in [Section 5](#) of this protocol and [Table 1](#).

All assessments should be performed prior to drug administration unless it is specified.

Visit 2/Day 1

Procedures at Visit 2/Day 1 should preferably be done in the sequence specified. Drug administration and blood sampling should adhere as closely as possible to the time schedule given in [Table 1](#)

- Urine pregnancy test, if applicable
- Review of inclusion and exclusion criteria
- Collect the filled diary card from patient
- Physician Global Assessment
- Partial Mayo Clinic Score assessment
- Concomitant medications
- Adverse events
- Full physical examination including weight and vitals
- Safety lab tests (Hematology and Chemistry)
- Urinalysis
- Blood sampling for anti-drug antibody (ADA) test at -15 min (prior to Neihulizumab infusion)
- PK sampling: -15min (prior to Neihulizumab infusion), and 2 hrs after the end of Neihulizumab infusion

- Administration of Neihulizumab: Study drug will be administered by approximately 1hr (60-minute) i.v. infusion. Patients should remain at the clinical site for at least 1 hour after the infusion for observation.

Visit 3/Day 8, Visit 4/Day 15, Visit 5/Day 22, Visit 7/Day 36, Visit 8/Day 43, Visit 9/Day 50, and Visit 11/Day 78

- Urine pregnancy test, if applicable
- Concomitant medications
- Adverse events
- Partial physical examination including, weight and vitals
- Collect the filled diary card from patient
- Physician Global Assessment
- Partial Mayo Clinic Score assessment
- Safety lab tests (Hematology and Chemistry)
- PK sampling: -15min (prior to Neihulizumab infusion) and 2 hrs after the end of Neihulizumab infusion for Visit 9 and 11. Fifteen (15) minutes prior to Neihulizumab infusion for Visits 3, 4, 5, 7 and 8
- Administration of Neihulizumab: Study drug will be administered by approximately 1hr (60-minute) i.v. infusion. Patients should remain at the clinical site for at least 1 hour after the infusion for observation.

Visit 6/Day 29 and Visit 10/Day 64

- Urine pregnancy test, if applicable
- Concomitant medications
- Adverse events
- Partial physical examination including weight and vitals
- Collect the filled diary card from patient
- Physician Global Assessment
- Partial Mayo Clinic Score assessment
- Safety lab tests (Hematology and Chemistry)
- Urinalysis
- Fecal calprotectin and CRP tests
- Blood sampling for anti-drug antibody (ADA) test at -15min (prior to Neihulizumab infusion)

- PK sampling: Fifteen minutes prior to Neihulizumab infusion (-15 min).
- Administration of Neihulizumab: Study drug will be administered by approximately 1hr (60-minute) i.v. infusion. Patients should remain at the clinical site for at least 1 hour after the infusion for observation.

Visit 12/Day 84 (End of Treatment)

- Urine pregnancy test, if applicable
- Concomitant medications
- Adverse events
- Full physical examination including weight and vitals
- Flexible sigmoidoscopy
- Collect the filled diary card from patient
- Physician Global Assessment
- Complete Mayo Clinic Score assessment
- Histopathological analysis
- IBDQ assessment
- Fecal calprotectin and CRP assessments
- PK sampling
- Safety lab tests (Hematology and Chemistry)
- Urinalysis
- Blood sampling for anti-drug antibody (ADA) test

Visit 13/ Day 112 and Visit 14/Day 140

- Concomitant medications
- Adverse events
- Partial physical examination including vitals
- Collect the filled diary card from patient
- Physician Global Assessment
- Partial Mayo Clinic Score assessment
- Fecal calprotectin and CRP tests
- Blood sampling for anti-drug antibody (ADA) test.
- Safety lab tests (Hematology and Chemistry)
- Urinalysis
- PK sampling

Visit 15/Day 182 (End of Study)

- Urine pregnancy test, if applicable
- Concomitant medications
- Adverse events
- Full physical examination including vitals
- Flexible sigmoidoscopy
- Collect the filled diary card from patient
- Physician Global Assessment
- Complete Mayo Clinic Score assessment
- Histopathological analysis
- IBDQ assessment
- Fecal calprotectin and CRP tests
- Safety lab tests (Hematology and Chemistry)
- Urinalysis
- Blood sampling for anti-drug antibody (ADA) test

7. STATISTICAL CONSIDERATIONS

This is a phase II, open labelled, multiple dose study to be held at multiple study centers. The trial was designed to assess the efficacy and safety of Neihulizumab treatment in moderate-severe ulcerative colitis patients. Due to the small number of patients expected to be enrolled at each center, all summaries and analyses will be performed using data pooled across centers. Unless otherwise specified, continuous variables will be summarized with the number of non-missing observations, mean, standard deviation, median, maximum and minimum displayed. Categorical data will be summarized as counts and percentages. Missing data will not be estimated or carried forward in any of the analyses.

Patient data will be listed, sorted by investigative center and patient number. Deviations from the statistical analysis plan will be documented in the clinical trial report.

Except where other software may be deemed more appropriate (e.g., S-Plus or R), all analyses will be performed using SAS Version 9.2 statistical software (SAS Institute, Cary, NC). Details of the statistical analysis (beyond those specified below) will be defined in the TSAP.

7.1 PLANNED ANALYSES

Intent to Treated Set

The ITT set is defined as all patients who are enrolled irrespective of treatment received or not.

Modified ITT (or Analyzable Set)

The mITT set is defined as all patients who are enrolled and have received at least one dose of Neihulizumab treatment.

The statistical analysis will be based on the modified ITT set. Summaries of patient disposition, demographics, disease characteristics, assessments of physical condition and functionality, and dosing of study drug will be provided.

7.1.1 Pharmacokinetic analyses

The following PK parameters will be assessed:

1. C_{max} ,
2. Any additional parameters as relevant

The PK profile will be monitored as specified in [Table 1](#) till Day 140 so that the profile of C_{max} and associated parameters can be determined.

All evaluable patients who received Neihulizumab will be included in the pharmacokinetic analysis. Patients who are considered as not evaluable will be listed with their individual plasma concentrations and individual pharmacokinetic parameters, however, will not be included in descriptive statistics for plasma concentrations, pharmacokinetic parameters or other statistical assessment.

A patient is considered to be not evaluable if the patient has a protocol violation relevant to the evaluation of pharmacokinetics.

Drug plasma concentrations

Concentrations will be used for graphs and calculations in the format that is reported in the bioanalytical report. Only concentrations within the validated concentration range will be used for the calculation of pharmacokinetic parameters.

Plasma concentrations will be plotted graphically versus time for all patients as listed in the drug plasma concentration-time tables. For the presentation of the mean profiles, the arithmetic mean, geometric mean and the planned blood sampling times will be used.

Drug plasma concentrations and pharmacokinetic parameters

The following descriptive statistics will be calculated for analyte concentrations as well as for all pharmacokinetic parameters: N, arithmetic mean, standard deviation, minimum, median, maximum, arithmetic coefficient of variation, geometric mean, geometric coefficient of variation.

The data format for descriptive statistics of concentrations will be identical with the data format of the respective concentrations. The descriptive statistics of pharmacokinetic parameters will be calculated using the individual values with the number of decimal places as provided by the evaluation program. Then the individual values as well as the descriptive statistics will be reported with three significant digits in the clinical trial report.

7.1.2 Safety analyses

Safety analyses will be performed based on the mITT set. No hypothesis testing is planned prospectively.

Adverse events will be coded using the Medical Dictionary for Drug Regulatory Affairs (MedDRA). Adverse events occurring prior to drug administration will be assigned to the screening period. All other adverse events will be assigned to the treatment periods for evaluation.

Independent of this rule, the relationship of an adverse event to the study drug treatment will be assessed by the investigator. The evaluation of adverse events will comprise various frequency tabulations.

Descriptive statistics of demographic data, of time-courses and of changes from baseline of vital signs and physical examination will be provided.

Descriptive statistics of laboratory values over time and for the difference from baseline will be provided. Frequency tables of changes with respect to the reference range between baseline and last value on treatment will also be presented.

Relevant findings in ECG measurements will be reported under “Relevant Medical History /Baseline Conditions” (at screening).

7.1.3 Efficacy analyses

Efficacy analyses will be performed based on the mITT set.

Summary statistics for efficacy endpoints will be provided.

7.1.4 Anti-drug Antibody

Human ADA concentrations will be determined by an ADA ELISA. The plate-specific, screening assay cut point will be set by a statistician to achieve a 5% false positive rate and was derived from assays using samples from naïve human donors. Study samples screened with signals below the cut point will be deemed negative for the presence of ADA, while samples at or above the cut point will be deemed putative positive for the presence of ADA.

All putative positive samples will be analyzed in a confirmation assay which is designed to test whether an excess of Neihulizumab added to the putative positive sample can inhibit the Neihulizumab response by a percentage greater than or equal to the confirmation cut point, thus confirming the presence of specific Neihulizumab antibodies. In addition, a titer, defined as the reciprocal of the lowest dilution of the sample whose signal fell below the cut point, will be determined for those samples that were confirmed to be positive for ADA.

A listing will be made of all patients with ADA values above the established cutoff level, along with their titers.

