Name of finished product: Neihulizumab			
Name of active ingredient: AbGn-168H			
Protocol date (Original): 2017.09.26	Trial number: 2017.008.01		Revision date (Amendment 4): 2018.11.01
Criteria for safety:	Physical examination, vital signs, safety laboratory tests, adverse events and tolerability.		
Pharmacokinetics parameters:	C _{max} and associated parameters		
Immunogenicity:	The Immunogenicity (anti-drug antibody; ADA) of AbGn-168H will be evaluated by a qualitative bridging immunoassay with electrochemiluminescence detection.		
Statistical methods:	
Determination of sample size: Assuming placebo effects of 25% (historical data) and AbGn-168H responsive rate of 45%, 40 patients have > 80% power to detect an alpha of 0.1 (two sided).
 
All patients who receive AbGn-168H treatment (modified Intent to Treat set, mITT) will be included in all analyses.
 
Summaries of patient disposition, demographics, disease characteristics, assessments of physical condition and functionality. Summary statistics for the time from the first dosing date to the last dosing date will be provided as the extent of drug exposure.
 
Descriptive statistics with appropriate plots will be employed in the analysis of all efficacy, PK, PD biomarkers (Fecal calprotectin and CRP), and immunogenicity (ADA) data.
 
AEs will be listed by body system using MedDRA terms. Descriptive statistics will be provided for clinical laboratory test results by scheduled time of evaluation, as well as for the change from baseline.
 
Summary statistics of continuous variables including numbers, means, standard deviations, median, minimum and maximum will be calculated. Categorical variables will be presented as number and percentages.
		

CLINICAL STUDY PROTOCOL APPROVAL/ACKNOWLEDGMENT

APPROVAL STATEMENT OF ABGENOMICS

On behalf of AbGenomics, only the Sponsor Medical Monitor is authorized to approve the Clinical Study Protocol and any subsequent amendment(s).

The following person has approved this Clinical Study Protocol using signatures as presented below:

[name]

Sponsor Medical Monitor's Name (Print)

31 Oct 2018

Sponsor Medical Monitor's Signature

Date of Signature
(DD MMM YYYY)

APPROVAL STATEMENT OF THE LEAD INVESTIGATOR

It is the responsibility of the Lead Investigator to approve the Clinical Study Protocol and any subsequent amendment(s).

The following person has approved this Clinical Study Protocol using signatures as presented below:

[name]

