In the 4- and 13-week studies with AbGn-168H and AbGn-168, the highest dose level tested of 100 mg/kg was a NOAEL. At the NOAEL, AbGn-168H mean exposures on Day 25 in the 4-week intravenous study were approximately 5,230,000 ng/mL (C_{max}) and 308,500,000 ng-hr/mL (AUC_{0-72hr}) and mean exposures on Day 22 of the 4-week subcutaneous study were approximately 4,450,000 ng/mL (C_{max}) and 353,000,000 ng-hr/mL (AUC_{0-96hr}). Exposure levels of AbGn-168H in the 4-week study were comparable to levels of total AbGn-168 (intact + shuffled) in 4- and 13-week studies. The results of the 4-week studies in cynomolgus monkeys with AbGn-168H, including exposure levels, mirror those of 4- and 13-week repeat-dose toxicity studies with AbGn-168.

Clinical Studies

AbGn-168H was first tested in a single rising dose (SRD) **trial (Study 1304.1)**[\[49\]](#) in 36 healthy volunteers in doses up to 2000 µg/kg i.v. and 125 and 1000 µg/kg s.c.. AbGn-168H was well tolerated in the SRD trial. There was no evidence of cytokine release and no critical change in laboratory parameters.

The PK analysis of trial 1304.1 demonstrated that no shuffling with AbGn-168H occurred. After i.v. dosing, AbGn-168H C_{max} or $AUC_{0-\infty}$ exposure increased in a close to dose-proportional manner. The terminal half-life of the antibody increased somewhat with dose up to the 500 µg/kg dose and then remained relatively constant at higher doses (40-45 h), which is relatively short compared to published values of endogenous IgG₄ half-life. This suggests that AbGn-168H may be cleared by target-mediated clearance. Following s.c. dosing, bioavailability for the 125 µg/kg

and 1000 µg/kg s.c. doses of AbGn-168H is 33% and 42%, respectively. These values may be relatively low because of the relatively rapid clearance of AbGn-168H. In trial 1304.1, Anti-Drug Antibody (ADA) responses were only observed in 1 subject dosed at 125 µg/kg s.c. AbGn-168H.

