Analysis of the pharmacokinetic parameters for AbGn-168H revealed that increasing the concentration of AbGn-168H from 6 mg/kg to 9 mg/kg increased both the plasma concentration and exposure (approximately 2.8 times). The steady-state $T_{1/2}$ was also increased from 113.9 hr in the AbGn-168H 6 mg/kg group to 132.1 hr in the AbGn-168H 9 mg/kg group. Of the 17 patients in the AbGn-168H 6 mg/kg group and the 16 patients in the AbGn-168H 9 mg/kg group, 4 (23.5%) patients in the AbGn-168H 6 mg/kg group and 5 (31.2%) patients in the AbGn-168H

9 mg/kg group were confirmed ADA positive at some time during the study. The ADA titer was generally low (≤ 3125) with the exception of 1 patient in the 9 mg/kg group who had an ADA titer of 15625 at Week 20.

Study 2014.009.01 is a phase II open-label, multi-center, proof of principle trial for psoriatic arthritis in which Seven (7) doses of AbGn-168H at 9 mg/kg was administered in 20 patients with moderately to severely active psoriatic arthritis. AbGn-168H were well tolerated and no safety concerns for AbGn-168H administration at this dose. Forty percent (40%) of all patients treated with study agent in this open label study demonstrated meaningful responses by week 12, suggesting the clinical utility with AbGn-168H for the treatment of psoriatic arthritis. **Clinical proof of principle is considered proven also for psoriatic arthritis [47]**. There was only one positive ADA response (Ab titer is 125) detected at Week 12 from 1 patient who had received all 7 doses of the study drug.

Since AbGn-168H demonstrated proof of clinical principle in treating T-cell mediated diseases such as psoriasis and psoriatic arthritis, a dose escalation/de-escalation study using AbGn-168H to treat steroid-refractory acute graft-versus-host disease (sr-aGvHD) in patients undergoing allogeneic hematopoietic cell transplantation was initiated (**Study BMT-285**). Patients received up to 4 infusions of up to 9 mg/kg of AbGn-168H. Four (4) patients were enrolled and received at least one infusion of AbGn-168H.

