The highest dose of AbGn-168H used in the 4-week intravenous and subcutaneous toxicity studies (100 mg/kg; twice weekly) was also the NOAEL. [Table 4](#) depicts safety margins extrapolated from 4th doses of AbGn-168H in humans (Study 2012.005.01 and Study 2014.002.01) *versus* the monkey NOAEL weekly dose and systemic exposure after 4-weeks of intravenous dosing. Although an adverse effect level was not reached with AbGn-168H in monkeys, it is clear that safety margins projected for the highest dose of 9 mg/kg based on body weight dose, C_{max}, and AUC comparisons for patients in this Phase I trial should be considered adequate. Safety evaluation from Study 2014.009.01 which was only 1 dose less than dosing regimen proposed in study also substantiates the safety of the current 8 dose regimen.

Table 4 Safety Margins from 4-Week Monkey Study (IV) with AbGn-168H estimated based on trial 2014.002.01

Species	Route of Admin	Maximum Dose	Weekly Dose	Dosing duration	C _{max} (ng/mL)	AUC (ng·hr/mL)	Safety Margins Vs Maximum Human Dose		
							Weekly Dose	C _{max}	AUC
Monkey	IV	100 mg/kg	200 mg/kg	4 weeks	5,230,000	308,500,000			
Human Patients	IV	9 mg/kg	9 mg/kg	8 weeks	751,750*	151,862,500*	>22X	>6X	>2X

*extrapolated data from 4st doses in Phase II studies (Study 2014.002.01) in psoriatic patients at 9 mg/kg iv.

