3. DESCRIPTION OF DESIGN AND TRIAL POPULATION

3.1 OVERALL TRIAL DESIGN AND PLAN

This will be an open label, multiple dose, multi-centre study to be conducted in around 12-18 centres in 30-40 patients with a diagnosis of moderate to severe active ulcerative colitis, refractory or intolerant to anti-TNF α and/or anti-integrin treatments.

Dose of Neihulizumab will be 9 mg/kg iv. Patients will receive a total of 10 doses on Day 1 (Week 0), Day 8 (Week 1), Day 15 (Week 2), Day 22 (Week 3), Day 29 (Week 4), Day 36 (Week 5), Day 43 (Week 6), Day 50 (Week 7), Day 64 (Week 9) and Day 78 (Week 11). Patients will be followed up on Day 84 (Week 12, End of Treatment, primary endpoint), Day 112 (Week 16), Day 140 (Week 20) and Day 182 (Week 26, End of Study) after the first dose of Neihulizumab.

In some case, patient may be allowed to continue the treatment of study drug in the judgment of the investigator and sponsor medical monitor.

Blood samples for PK determinations will be drawn approximately 15 minutes before dosing and 2 hours post doing at Visits 2, 9 and 11, 15 minutes before doing at Visits 3, 4, 5, 6, 7, 8 and 10, and at Visits 12, 13 and 14. Anti-drug antibodies (ADA) will be determined in all patients before dosing at Visits 2, 6, 10 and at Visits 12-15. Efficacy will be assessed by Mayo Clinic Score (Complete and Partial), endoscopy, biopsy, Inflammatory Bowel Disease Questionnaire (IBDQ) and Biomarkers (faecal calprotectin and c-reactive protein). Safety will be assessed by adverse event (AE) monitoring, laboratory tests, vital signs, physical examinations, discontinuation of treatment due to AE and immunogenicity.

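### Samples below the cut point are called ADA-negative whatever the drug level in them; on-treatment negatives could be masked positives, and reading them against the paired PK samples is a cheap improvement

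*Protocol*

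**What the plan says.** Immunogenicity is part of the secondary objective (Protocol 2.2, SAP 3.2) and a safety endpoint (Protocol 5.2.1). The only rule for classifying samples is in Protocol 7.1.4: "Study samples screened with signals below the cut point will be deemed negative for the presence of ADA". The cut point is set from naïve donors for a 5% false-positive rate. Samples at or above it go to a confirmation assay, in which extra Neihulizumab is added to see whether it inhibits the response. Only patients above the cutoff are to be listed, with titers. There is no condition on drug concentration, no drug-tolerance limit and no inconclusive category. SAP section 2 excludes ADA from its analyses, and SAP 5.12 defers to a bioanalytical report.

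Sampling is set in Protocol 3.1: "Anti-drug antibodies (ADA) will be determined in all patients before dosing at Visits 2, 6, 10 and at Visits 12-15". Under Amendment 4, Table 1 makes these Days 1, 29, 64, 84, 112, 140 and 182.

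Two descriptions do not agree:
- **Assay.** Section 7.1.4 says "Human ADA concentrations will be determined by an ADA ELISA", while the synopsis says ADA "will be evaluated by a qualitative bridging immunoassay with electrochemiluminescence detection".
- **Day.** Section 5.3 places samples "before Neihulizumab administration on Day 1, Day 29, Day 57 and also at EOT (Day 84", but Amendment 4 has no Day 57 visit; Visit 10 is Day 64.

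**The concern.** The confirmation step works because free drug competes for the antibody and lowers the signal. Drug circulating at the time of sampling can have the same effect before the screening step, and a cut point from drug-naïve donors does not allow for it. A negative drawn at high drug concentration may then mean either no antibody or antibody that the assay could not see.

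This matters most for patients with no late sample. Protocol 3.3.4.1 requires treatment withdrawal after a rise of 2 or more in the partial Mayo score, 4.2 after a grade 3 to 5 hypersensitivity reaction, and 4.3.2 requires trial withdrawal after restricted medication for worsening colitis. If such a patient stops attending, Table 1 footnote 1 makes the last visit the EOS visit. That ADA sample may follow a dose closely, and Amendment 4 schedules no PK sample at EOS. ADA could then be missed in the patients for whom a link with reactions or loss of effect would be most informative.

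**Working it through.** **Inputs**
- Human peak at 9 mg/kg: 751,750 ng/mL = 751.75 µg/mL (Protocol Table 4), extrapolated from the fourth dose of Study 2014.002.01 "in psoriatic patients at 9 mg/kg iv".
- Half-life: "113.9 hr in the AbGn-168H 6 mg/kg group to 132.1 hr in the AbGn-168H 9 mg/kg group" (Protocol 1.2). As a short extreme, the healthy-volunteer value at doses up to 2 mg/kg, which "then remained relatively constant at higher doses (40-45 h").
- Amendment 4 dose days: 1, 8, 15, 22, 29, 36, 43, 50, 64, 78. Study 2014.002.01 dose days: 1, 8, 29, 36.
- Drug tolerance of the assay: in neither document, so an assumption.

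**Reproducing Table 4.** 200/9 = 22.2; 5,230,000/751,750 = 6.96; 308,500,000/151,862,500 = 2.03. These match the stated margins of >22X, >6X and >2X and confirm the units. As a rough check on the half-life, ln 2 × 151,862,500/751,750 = 140 h, close to 132.1 h.

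**Peak from a single dose.** Each dose is taken to decay as 2^(−24d/T½), with d in days. At the fourth dose in Study 2014.002.01 (T½ 132.1 h) the accumulation factor is 1 + 2^(−168/132.1) + 2^(−672/132.1) + 2^(−840/132.1) = 1 + 0.414 + 0.029 + 0.012 = 1.456. The single-dose peak is 751.75/1.456 = 516 µg/mL.

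**Drug level at each ADA visit.** This is 516 µg/mL times the sum of the decay factors of all earlier doses. On Day 29, for example, the sum is 0.414 + 0.172 + 0.071 + 0.029 = 0.686, giving 354 µg/mL. Each column below recomputes the accumulation factor for its half-life.

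| Day | Days since last dose | Relative level (132.1 h) | µg/mL, 132.1 h | µg/mL, 113.9 h | µg/mL, 45 h |
|---|---|---|---|---|---|
| 29 | 7 | 0.686 | 354 | 300 | 57 |
| 64 | 14 | 0.293 | 151 | 110 | 4 |
| 84 | 6 | 0.574 | 296 | 262 | 77 |
| 112 | 34 | 0.0169 | 8.7 | 4.4 | 0.002 |
| 140 | 62 | 0.0005 | 0.26 | 0.07 | about 0 |
| 182 | 104 | about 0 | 0.001 | about 0 | about 0 |

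A simpler check, decaying the full 751.75 µg/mL from the last dose only at 132.1 h, gives 311, 129 and 353 µg/mL on Days 29, 64 and 84. On the Amendments 1-3 schedule (SAP Appendix 2) superposition at 132.1 h gives 354, 114 and 122 µg/mL on Days 29, 57 and 84.

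**Lower extremes.** If the Table 4 peak is three times too high, Days 29, 64 and 84 become 118, 50 and 99 µg/mL. With a 45 h half-life as well, they are about 19, 1.4 and 26.

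**What this means for negatives, by assumed tolerance (132.1 h column).**

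| Tolerance, µg/mL | Post-baseline samples above it (of 6) |
|---|---|
| 1 | 4 (Days 29, 64, 84, 112) |
| 10, 50 or 100 | 3 (Days 29, 64, 84) |
| 200 | 2 (Days 29, 84) |
| 400 | 0 |

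Days 140 and 182 stay interpretable at any tolerance above about 0.26 µg/mL.

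**The case against.** The strongest objection is that the deciding figure is absent. Masking occurs only if drug exceeds the assay's tolerance, and that may be documented in the laboratory manual or bioanalytical report. With a tolerance of 400 µg/mL no scheduled sample would be affected in the base case. This stands, and it limits the point to an unaddressed risk.

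The predicted levels are also uncertain. They carry psoriasis data into colitis through a linear model, while Protocol 1.2 suggests target-mediated clearance and reports exposure rising out of proportion to dose. It is tempting to say that every on-treatment sample holds tens to hundreds of µg/mL; at 45 h, Day 64 holds about 4.

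A reader might also take earlier ADA rates as signs of masking: 38.9% at 3 mg/kg, 31.2% at 9 mg/kg, and 1 of 20 after seven 9 mg/kg doses. The documents do not support that. Within each psoriasis study positivity rose with dose (15.8% at 0.5 mg/kg against 38.9% at 3 mg/kg; 23.5% at 6 mg/kg against 31.2% at 9 mg/kg), which is not what masking would predict, and the comparison across studies mixes diseases and regimens.

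Finally, patients who stop treatment are encouraged to attend through EOS, and 7.1.4 classifies samples, not patients. So it does not follow that anyone who leaves treatment has only on-drug samples or is counted negative by rule. The exposure is confined to those who also leave follow-up, and to transient antibodies and the timing of onset in the others.

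**Conclusion.** The rule in 7.1.4 is incomplete on its own logic, and nothing else in the two documents repairs it. In the base case three of the six post-baseline samples (Days 29, 64 and 84) contain about 150 to 350 µg/mL of drug, and a negative there is uninformative if the assay tolerates less. This rests on the Table 4 peak, the 132.1 h half-life, mono-exponential superposition and an unknown tolerance.

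The stronger inference, that ADA will be under-counted, is not supported: tolerance is unstated, and Days 140 and 182 can recover persistent ADA in patients followed to then. This is a cheap improvement to classification and reporting. The assay and Day 57 mismatches are editorial; Day 57 was an ADA visit under Amendments 1-3.

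**What to change.** 1. **Classification (7.1.4).** Call a below-cut-point sample negative only if the concurrent drug concentration is below the assay's validated drug tolerance, and otherwise inconclusive. State the tolerance.
2. **Listing.** List all ADA results, not only positives, beside the paired PK concentration. Amendment 4 already collects it at every ADA visit except Day 182.
3. **No paired PK sample.** For Day 182 or an early EOS, judge by time since last dose and not by the visit label.
4. **Reporting.** Show positive, negative and inconclusive patients separately. Give ADA incidence over all treated patients with a post-baseline sample (a lower bound) and over evaluable patients. Split on-treatment from washout samples.
5. **Editorial.** Name one assay in the synopsis and 7.1.4, and reconcile Day 57 in 5.3 with Visit 10/Day 64 in Table 1.

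Both incidence figures are needed because a positive counts on any sample while a negative needs a low-drug one, so the evaluable figure can overstate incidence. As an illustration, 4 positive and 6 inconclusive among 20 patients gives 4/20 = 20% and 4/14 = 29%.

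The cost is wording and a fuller listing, with no new samples, provided that a validated tolerance exists. Some patients become inconclusive, the evaluable denominator shrinks, and the two incidence figures may differ.
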